PROSPER PROTOCOL

PROSPER (Patient-centered Research into Outcomes Stroke patients Prefer and Effectiveness Research) is a three year research project to create a national, sustainable model to improve decision-making and patient-centered stroke outcomes through comparative effectiveness research.

PROSPER

(Patient-centered Research into Outcomes Stroke patients Prefer and Effectiveness Research)

Table of Contents

Introduction..... 3

Objectives..... 3

Design and Procedures..... 4

Study outcomes 4

Site selection 4

Site/Investigator Obligations 5

Subject selection 5

Inclusion criteria 5

Exclusion criteria 5

Ethical Considerations 6

Consent Process 6

Capacity to give legally effective consent 6

Risk/benefit assessment 7

Costs to the subject/compensation 7

Statistical Considerations 7

Governance 8

Appendix 10

.....

CONFIDENTIAL

The information contained in this proposal is confidential and the property of Duke University. It is intended solely for the use of the recipient in evaluating whether or not to enter into a participation agreement with Duke University or for site personnel training, and not for any other purpose. This information is not to be distributed outside the recipient organization.

PROSPER

(Patient-centered Research into Outcomes Stroke patients Prefer and Effectiveness Research)

Introduction

Stroke is the fourth leading cause of death and the most common cause of long-term disability in the United States. Every 40 seconds, someone in the US has a stroke, with almost 1/4 of these being recurrent strokes. The burden of stroke is disproportionately borne by older patients, women and blacks. The prognosis after stroke remains poor, with 1-year mortality rate of 15-30%. Stroke is the second most common reason for hospitalization among those 65 years or older and the leading cause of long-term disability. After stroke, there are large variations in care, and patients have significant uncertainties regarding the balance of benefits and risks of medications prescribed. To date, clinical trials have enrolled highly selected patients that are not representative of the broader stroke community. This leaves many questions unanswered for real-world stroke survivors on what therapies will have the greatest impact on their well-being.

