Contact information for telephone interviews will be accessible only to specified interviewing personal via a password protected mechanism. Collected telephone interview data will be stored in separate tables using the unique study identifier, as the primary key. These data will not be tied to the PHI collected as part of the contact information. All interview data will be stored on a password protected server and adhere to DCRI electronic safeguards.

Statistical Considerations

PROSPER will apply statistical protocols with pre-specified inclusion/exclusion criteria, analytic plans and sensitivity analyses. The analytic framework for PROSPER will, in general, utilize a “causal inference method”, or propensity scoring methods, to compare the safety and effectiveness of two or more stroke prevention, treatment, and management strategies. Standardized difference will be used to assess the balance across compared groups with respect to potential confounding variables in propensity score analysis.

Our primary end point, “home time”, will be analyzed using a linear regression model with transformations as necessary. Time to event outcomes (e.g. time-to-death, time to readmission) will be analyzed using the Cox proportional hazard model. Based on the models, the Wald’s tests will be used to test the significance of the treatment effects. After fitting models, the marginal residuals from the model will be used to test the goodness-of-fit of the proportional hazards model, with special attention to the proportionality assumption. When this assumption is not supported by the data, possible treatment and time interactions and other possible time-dependent covariates will be used to account for this non-proportionality. The resulting p-values that are less than 5% will be considered evidence of significant marginal differences across the cohorts.

Dichotomous outcomes (e.g. mRS, death, readmission) and continuous outcomes (e.g. Barthel Index, home time as a continuous measure) will be analyzed using multivariate logistic regression and multivariable linear regression models. We will perform subgroup analyses and/or advanced statistical modeling to determine the possible interaction between the treatment and patient characteristics and estimate the heterogeneity of treatment effects to reflect the individualization of results from the analyses. Our analyses will also account for clustering of patients within hospitals using generalized estimating equations (GEE).

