Hospital characteristics				
Teaching status				
Rural location				
Region				
Primary Stroke Centers				
Comprehensive Stroke Centers				
Hospital size, mean (SD)				
Annual IS admission volume, mean (SD)				

All numbers presented are proportions of patient in the study population, unless specified otherwise.

\* P-values from chi-squared tests for independence for categorical variables and Wilcoxon rank sum tests for continuous variables

## 2. Objective 2

**Aim:** To estimate the associations between antidepressant use (any vs. none) and outcomes (home time, all-cause mortality, all-cause readmission recurrent stroke [ischemic, hemorrhagic], cardiovascular rehospitalization, and depression-related hospitalization [suicidality or major depressive episode] following discharge).

**Analysis:** Because patients who receive AD may differ from those who do not on important baseline and clinical characteristics that may affect the likelihood of adverse events, we will use inverse probability of treatment weighting (IPW) when assessing treatment effects. IPT weighting will be accomplished in two steps: First, we will use a logistic regression model to assign a probability of treatment selection to each patient based on the distribution of a defined set of covariates (listed above). The binary outcome for the selection model will be AD treatment (Y/N). In the second step, we will weight subject by the inverse of this assigned treatment probability, resulting in a pseudo-randomization of patients to AD vs. no AD treatment. The distribution of baseline patient characteristics for each treatment group will be assessed after weighting to determine adequacy of the selection model.

Following IPW, we will compare primary and secondary endpoints between treatment groups. Unadjusted rates of all-cause mortality, all-cause readmission, CV readmission, depression-related admission and stroke/TIA readmission will be examined using a Cox proportional hazards model with AD use as the single independent variable. Adjusted event rates will then be estimated using the same model with IPW included for each subject. Within-hospital clustering will be accounted for using robust estimator approach.

Home time will be examined first as a continuous variable in a linear regression model and then as a dichotomous outcome in an IPW-weighted logistic regression model, using 100% of time spent at home over 1 year as the primary outcome of interest.

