Methods will be repeated for SSRI vs. non-SSRI with corresponding modeling of clinical outcomes.

**Output:** [Table 2](#) (AD vs No AD), [Table 3](#) (SSRI vs not SSRI)

**Table 2.** AD use and clinical outcomes following ischemic stroke discharge.

Outcomes	AD	No AD (ref)	Unadjusted HR (95% CI)	Adjusted HR (95% CI)	P-value
----------	----	----------------	---------------------------	-------------------------	---------

**Table 3.** SSRI vs. non-SSRI use and clinical outcomes following ischemic stroke discharge.

Outcomes	SSRI	Other AD (ref)	Unadjusted HR (95% CI)	Adjusted HR (95% CI)	P-value
Home time: 100% (OR)					
All-cause mortality					
Readmission					
All-cause					
Cardiovascular					
Stroke/TIA					
Ischemic Stroke					
Hemorrhagic Stroke					
Depression-related readmission					
			Unadjusted Difference (95% CI)	Adjusted Difference (95% CI)	
Home time days, mean (SD)					

[figure not shown]
### 3. Objective 3

**Aim:** To describe 1y mortality and readmission outcomes by plotting the cumulative incidence functions.

**Analysis:** We will limit the population to patients naïve to AD on admission and construct Kaplan-Meier curves for all-cause mortality at 1 year following the index hospitalization for patients prescribed AD at hospital discharge. Log-rank tests will be used to examine mortality differences between AD treatment groups.

For the other non-mortality endpoints, we will calculate incidence at 1 year based on estimates from the cumulative incidence function, to account for the competing risk of mortality. Gray tests will be used to test for differences between groups for these outcomes.

We will then restrict the study population to patients receiving AD at hospital discharge and analyses will be repeated for SSRI vs. non-SSRI antidepressants.

**Figure X.** Cumulative incidence plots for mortality and readmissions by AD types (Yes vs No, and again for SSRI vs Non-SSRI).

### 4. Objective 4

**Aim:** Perform subgroup analyses.

**Analysis:** Because AD use and outcomes may vary by patient characteristics, we will repeat modeling of these associations by the following subgroups: Age (65-80, 80-90, 90+), sex (male vs. female), race (white vs. non-white), NIH stroke scale (<16 vs. ≥16), and medical history of depression.

Repeat Tables 2 and 3 in subgroups defined.

### 5. Objective 5

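### Objective 2 takes adjusted readmission rates from a weighted Cox model with no provision for death as a competing event, and Objective 3 does not supply the missing adjusted rates

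*SAP*

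**What the plan says.** **SAP III, Objective 2.** Unadjusted rates of all-cause mortality and of all-cause, cardiovascular, depression-related and stroke/TIA readmission "will be examined using a Cox proportional hazards model with AD use as the single independent variable". The next sentence is: "Adjusted event rates will then be estimated using the same model with IPW included for each subject". Within-hospital clustering is handled with a robust estimator. The section gives no censoring rule for death, names no competing-risk method, and sets no time horizon for these endpoints; the one-year period it mentions belongs to home time.

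**SAP Tables 2 and 3.** The shells have one column per treatment group, then an unadjusted and an adjusted hazard ratio. They do not say what the group columns hold for the time-to-event endpoints.

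**SAP III, Objective 3.** For non-mortality endpoints, "we will calculate incidence at 1 year based on estimates from the cumulative incidence function, to account for the competing risk of mortality". The comparison is specified too: "Gray tests will be used to test for differences between groups for these outcomes". The population is restricted: "We will limit the population to patients naïve to AD on admission". No weighting is mentioned.

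**Protocol, Statistical Considerations.** "Time to event outcomes (e.g. time-to-death, time to readmission) will be analyzed using the Cox proportional hazard model". No competing-risk method is named there either.

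**Protocol, Introduction.** Stroke prognosis is described with a "1-year mortality rate of 15-30" percent, as general background.

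**The concern.** In a standard Cox model for time to readmission, a patient who dies first is censored. The hazard ratio then compares readmission hazards among patients still alive and not yet readmitted, which is a legitimate quantity. A rate obtained as 1-S(t) from that model is different: it is the risk that would apply if nobody could die before readmission, so it exceeds the proportion of patients who are actually readmitted.

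The SAP accepts this reasoning in Objective 3 but does not carry it into Objective 2, where the adjusted comparison is made. Two things are at stake. Absolute readmission risks could be reported too high. And if mortality differs between the AD groups, which Objective 2 itself examines, the excess differs by group, so a comparison of those rates is distorted as well. Absolute risks may be used later: Protocol Aim 3 plans decision aids from the comparative studies, and the Protocol's section on educational forums includes individual risk prediction among the tool content.

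**Working it through.** The documents give no readmission rate or event count for this analysis, so there is no planned figure to reproduce.

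**1. Does Objective 3 fill the gap?** In the SAP's exposure tables, 1,836 of the 7,593 patients discharged on an AD are recorded as not taking one before admission: 1,836/7,593 = 24.2%. Among patients discharged without an AD the figure is 20,601/21,584 = 95.4%. The Objective 3 incidence therefore leaves out about three quarters of the treated group. It is also unweighted as written, so no adjusted cumulative incidence is planned in any population.

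**2. Size of the excess.** Inputs:
- 1-year mortality m = 15% and 30%, the ends of the Protocol's background range.
- 1-year readmission risk with death censored, p = 5% to 55%. This is an assumption, ranging from rare to common endpoints.
- Constant, independent hazards, with the death hazard before readmission set equal to the overall death hazard.

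Formulas:
- λr = -ln(1-p) and λd = -ln(1-m)
- Death-censored rate: 1 - exp(-λr) = p
- Cumulative incidence: λr/(λr+λd) × [1 - exp(-(λr+λd))]

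Example, p = 20% and m = 15%: λr = 0.2231, λd = 0.1625. Cumulative incidence = 0.2231/0.3857 × (1 - 0.80×0.85) = 0.5786 × 0.32 = 18.5%. The excess is 1.5 points, or 8.0% relative.

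| Death-censored rate | Cumulative incidence, 15% mortality | Excess: points (relative) | Cumulative incidence, 30% mortality | Excess: points (relative) |
|---|---|---|---|---|
| 5% | 4.6% | 0.4 (8.3%) | 4.2% | 0.8 (18.7%) |
| 20% | 18.5% | 1.5 (8.0%) | 16.9% | 3.1 (18.1%) |
| 40% | 37.2% | 2.8 (7.6%) | 34.2% | 5.8 (17.1%) |
| 55% | 51.3% | 3.7 (7.2%) | 47.3% | 7.7 (16.2%) |

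**3. Sensitivity to the mortality figure.** The SAP cohort excludes in-hospital deaths: 4,148 of the 73,633 patients remaining at that step, or 5.6%. If the 15-30% includes in-hospital deaths (an assumption), post-discharge mortality is (0.15-0.056)/(1-0.056) = 9.9% to (0.30-0.056)/(1-0.056) = 25.8%. With m rounded to 10% and 26%, the relative excess is about 5% and 14-16%.

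**4. Effect on a comparison.** Give both groups a readmission hazard of 0.6 per year (assumed), with 15% mortality in one and 30% in the other. The death-censored rate is 1 - exp(-0.6) = 45.1% in both, so no difference appears. The cumulative incidences are 42.0% and 38.6%, a gap of 3.4 points and a ratio of about 0.92, although the cause-specific hazard ratio is exactly 1. Both results are correct, but they answer different questions, so the SAP needs to say which one each table reports.

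**The case against.** The strongest reply is that the sentence on adjusted rates only repeats the preceding one with weights added, so rates may loosely mean hazards. The declared outputs fit this: the only adjusted column in Tables 2 and 3 for these endpoints is a hazard ratio, and Objective 2 never mentions a predicted risk. Where the SAP does explicitly plan 1-year readmission incidence, in Objective 3, it accounts for death. On this reading nothing planned is biased and only a clarification is due.

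Much of that stands. Three stronger conclusions that a reader might infer are not supported:
- **That the hazard ratios are biased.** They are valid as cause-specific hazard ratios and should stay.
- **That Objective 2 contradicts Objective 3.** Cause-specific hazard ratios and cumulative incidence curves are complementary, and the two objectives differ in purpose and population. They are unreconciled, not contradictory.
- **That this cohort has 15-30% annual mortality and its 1-year rates will be overstated by a known amount.** The range is background for stroke in general. Censoring at death and a 1-year horizon are inferred for Objective 2, and the readmission risks above are assumptions. If deaths cluster after readmission, the excess for all-cause readmission is smaller than shown. For rare endpoints it is under a point in absolute terms.

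The stakes are also bounded. The primary endpoint, home time, already counts only days alive; the readmission endpoints are secondary, and depression-related admission is exploratory. Nor do the documents say that the decision aids will use rates predicted from this model.

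What the reply does not remove is the text itself. It announces adjusted event rates from the Cox model, leaves the group columns undefined, and plans no weighted incidence elsewhere. An analyst following it literally would produce rates that are too high.

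**Conclusion.** The point holds as a gap in Objective 2: adjusted readmission rates are to come from a weighted Cox model with no stated handling of death, and the only analysis that does handle death covers a restricted population without weights. The consequence is conditional. It arises if absolute rates are read from that model with death censored, and then the relative excess is about 7-8% at 15% mortality and 16-19% at 30%, or about 5-16% if the background range includes in-hospital deaths. These figures rest on constant independent hazards and assumed readmission risks. The comparison by hazard ratio is unaffected. The change is worth making before analysis because it is cheap and the SAP already accepts the reason for it.

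**What to change.** In SAP Objective 2:

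1. State that the readmission hazard ratios are cause-specific, with death as a censoring event, and keep them.
2. Replace the Cox-derived event rates for the readmission endpoints with 1-year cumulative incidence, death as a competing event (Aalen-Johansen estimator), in the full Objective 2 population. Report it unadjusted and weighted with the treatment weights already planned, with intervals that respect clustering by hospital. Do the same for SSRI versus other AD with that comparison's own weights.
3. Define the group columns of Tables 2 and 3 as these incidences, and carry the definition into the subgroup repeats under Objective 4.
4. Add a sentence saying that Objective 3 describes the AD-naive subset, whether its curves are weighted, and that its Gray tests need not agree with the cause-specific hazard ratios.

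The cost is a few sentences of SAP text and a little extra analysis: existing weights applied to a method already planned for Objective 3. No new data are needed.

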### 3. Outcomes/Endpoints

#### Primary:

- Home-time: Total number of days spent alive and outside of a hospital, skilled nursing facility, or inpatient rehabilitation facility since discharge

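### The SAP names only a robust variance for its weighted analyses; in its usual form this ignores that the weights are estimated and tends to make adjusted confidence intervals too wide

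*SAP*

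**What the plan says.** SAP section III, Objective 2 builds the weights in two steps: "First, we will use a logistic regression model to assign a probability of treatment selection to each patient", and then "we will weight subject by the inverse of this assigned treatment probability". Mortality and readmission are compared "using a Cox proportional hazards model with AD use as the single independent variable", first unweighted and then with the weights. That paragraph ends: "Within-hospital clustering will be accounted for using robust estimator approach". Nothing is said about how the estimation of the weights enters the variance, and neither a bootstrap nor a stacked variance is mentioned.

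The next paragraph covers the primary endpoint: "Home time will be examined first as a continuous variable in a linear regression model and then as a dichotomous outcome". It names no variance method, and only the dichotomous model is called weighted. Two other places imply that home-time in days is weighted too. The Cox paragraph opens by saying that primary and secondary endpoints will be compared after weighting, and the results table has a row for an adjusted home-time difference with a 95% interval.

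The same methods are repeated for SSRI versus other antidepressants and in the subgroups. The protocol (Statistical Considerations) accounts for hospital clustering by GEE and is also silent on estimated weights.

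**The concern.** A robust variance computed from supplied weights treats them as fixed constants. Here they come from a fitted model. If that model contains predictors of the outcome, fitting it balances chance differences in those predictors between the groups, so the weighted contrast varies less from sample to sample than fixed weights would imply. The fixed-weight formula still counts the variation that has been removed, and the reported standard error tends to be too large.

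One sentence shapes many intervals: those for the secondary endpoints directly and, if it is read as general, those for home-time, the SSRI contrast (1,072 versus 446 patients) and every subgroup. The risk is that a real difference is reported as inconclusive.

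**Working it through.** The documents give no standard error, interval width or R², so there is no planned figure to reproduce. The check has a closed-form part and a simulated part.

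**Inputs from the SAP.** Final population: 29,177 patients in 1,023 hospitals. Antidepressant at discharge: 7,593 yes, 21,584 no. Prior use known for 28,869 patients. Discharge prescription probability e by prior use:
- prior users: 5,678/6,432 = 0.883, so e(1−e) = 0.103
- others: 1,836/22,437 = 0.082, so e(1−e) = 0.075

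**Assumptions, not in the documents.** R² of home-time on the covariates, the spread of home-time, an outcome intra-hospital correlation of 0.02, and how strongly the other covariates drive treatment.

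**Closed form.** Suppose the outcome predictors do not affect treatment given prior use. Estimating the weights then removes this fraction of the outcome variance that they explain:

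1 / {mean[e(1−e)] × mean[1/(e(1−e))]} = 1/(0.0814 × 12.50) = 0.98.

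Fixed-weight SE over true SE = 1/√(1 − 0.98·R²), which is 1.05, 1.12 and 1.19 at R² = 0.1, 0.2 and 0.3. For SSRI versus other (800/1,125 and 262/380) the fraction exceeds 0.999. This is close to a ceiling, because any effect of these covariates on treatment lowers it.

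**Simulation.** Same N and hospitals; treatment calibrated to the SAP's antidepressant, prior-use and depression margins; 20 further covariates that also affect treatment; correctly specified patient-level selection model; 1,000 data sets per row (antidepressant versus none).

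| R² | Home-time: fixed-weight SE / empirical SD | Home-time: fixed-weight SE / estimated-weight SE | Coverage of the 95% CI, home-time | Cox mortality: fixed-weight SE / estimated-weight SE |
|---|---|---|---|---|
| 0.06 | 1.01 | 1.03 | 94.8% | 1.01 |
| 0.10 | 1.03 | 1.05 | 95.2% | 1.02 |
| 0.19 | 1.07 | 1.10 | 95.9% | 1.04 |
| 0.27 | 1.13 | 1.15 | 96.8% | 1.06 |
| 0.36 | 1.19 | 1.21 | 97.9% | 1.08 |

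An empirical SD from 1,000 data sets carries about 1/√(2×999) = 2.2% Monte Carlo error, so the first two ratios to the empirical SD cannot be told from 1.00. The ratio of the two standard errors does not involve the empirical SD. The home-time SE that allows for estimated weights was 0.98 of the empirical SD throughout. For 100% home-time (logistic) the ratio to the empirical SD was 1.02 to 1.10. For SSRI versus other it was 1.02 to 1.21 for home-time and 1.01 to 1.10 for Cox.

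**Stronger selection.** With the other covariates three times as influential on treatment (largest weight about 220, 600 data sets), the ratio to the empirical SD falls to 0.99 (R² 0.10) and 1.04 (R² 0.27) for home-time, and to 1.00–1.01 for Cox. Weights are uneven even from prior use alone: 22,437/1,836 = 12.2 for treated patients without prior use and 6,432/754 = 8.5 for untreated prior users.

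**What the excess costs.** For an effect with true power of 80%, power becomes Φ(1.96 + 0.84 − 1.96r) at ratio r: 76%, 72% and 68% for r = 1.07, 1.13 and 1.19. At R² 0.27 the home-time half-width is 1.96 × 2.80 = 5.5 days instead of 1.96 × 2.49 = 4.9 for antidepressant versus none, and 1.96 × 7.18 = 14.1 instead of 1.96 × 6.26 = 12.3 for SSRI versus other. The figures in days depend on the assumed spread of home-time.

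**The case against.** The strongest reply is textual. The SAP never says that the weights are taken as known; this is inferred from its silence and from how the robust estimator usually works. The sentence belongs to the Cox paragraph, and so does the statement that treatment is the only regressor. The protocol assigns home-time as a continuous measure to multivariable linear regression, which could mean covariates in that model. All of this stands, and it makes the home-time part an inference. It does not remove the point: if the sentence does not reach home-time, the SAP has no variance method for its primary endpoint.

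The second reply concerns size. R² is assumed, a robust sandwich with weights is common and usually conservative, and the excess in days is modest. This also stands.

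Three stronger readings are tempting, and the documents do not support them.
- A reader might infer that home-time intervals are clearly too wide. That needs an R² that the documents do not give. Ratios as high as 1.47 for home-time (R² 0.5) and 1.19 for Cox have been simulated, but the home-time figures lie near the ceiling that applies when outcome predictors do not affect treatment. The SAP weights precisely because they may.
- A reader might infer that the intervals are always too wide. The direction relies on a correctly specified selection model, and the excess can vanish when weights are large.
- A reader might infer that covariates in the weighted linear model settle the matter. In runs with heavier weights, the robust SE from that model was 0.97 and 0.94 of the true SD, so slightly too small.

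**Conclusion.** The point holds in a qualified form. Followed in the usual way, the SAP's variance method tends to overstate the standard errors of the weighted results. For home-time the excess is roughly 1–5% at R² of 0.1 or less and about 10–20% near 0.3, with little or none when covariates strongly drive treatment and weights are large. For the Cox hazard ratios of antidepressant versus none it is about 1–8%.

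This rests on weights by the inverse probability of the treatment received, a correct selection model, the assumed R², and the inference that the robust sentence extends to home-time. Type I error is not inflated. What is lost is precision, and in absolute terms the loss is largest in the small SSRI comparison. It is a minor to moderate point, worth making because the remedy is cheap and does not depend on knowing R².

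**What to change.** State in SAP Objective 2 that the confidence interval for every weighted analysis comes from a bootstrap that resamples whole hospitals and refits the selection model in each resample. Name the analyses covered: home-time in days, 100% home-time, the Cox endpoints, the SSRI contrast and the subgroups. A stacked, hospital-clustered sandwich variance that includes the selection model's score equations is an acceptable alternative. Say explicitly that the linear model for home-time in days is weighted.

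The cost is a few sentences and computing time. The weighting and the estimand do not change.

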## 2. Other variables

Demographics: Age, race, gender, insurance status, medical history (depression, stroke, TIA, DM, CAD, AF, HF, HTN, PVD, smoking)

Presentation variables: EMS transport, ambulatory status, initial NIHSS, prior antidepressant use

In-hospital variables: Dysphagia screening, DVT prophylaxis, t-PA, t-PA date/time, VTE interventions, documented DVT/PE, antithrombotics by day 2

Discharge variables: Discharge disposition, ambulatory status at discharge, ICD-9 discharge diagnosis, Antiplatelet/anticoagulant/HTN/AD meds, stroke education, smoking cessation, assessment for rehabilitation services

Hospital variables: Primary stroke center; comprehensive stroke center, teaching status, hospital bed size, rural location, region, annual volume of IS admissions

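### Objective 6 aims to estimate how antidepressant use relates to patient-reported outcomes, but the SAP gives it no analysis and only unadjusted summaries; Objective 3's tests in AD-naive patients also state no adjustment.

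*SAP*

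**What the plan says.** **Objective 2 (SAP, III. Analysis Tasks).** The reason for adjustment is explicit: "Because patients who receive AD may differ from those who do not on important baseline and clinical characteristics" that may affect adverse events, "we will use inverse probability of treatment weighting (IPW) when assessing treatment effects". Weighted Cox, linear and logistic models follow, and "Within-hospital clustering will be accounted for using robust estimator approach". The covariates listed under Other variables include "initial NIHSS, prior antidepressant use" and history of depression.

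**Objective 6.** The aim is to estimate associations between any AD use and mRS, EQ-5D-3L, PHQ-2, SIS-16 and the Fatigue Severity Scale. Objectives 1 to 5 each have an Analysis paragraph; Objective 6 has none. Its outputs are a Grotta bar and Tables 6A to 6G, which hold percentages, means with standard errors, medians with quartiles, and percentages past a cut-off, by group and time point. No column holds a difference, interval, test or adjusted value. Objective 7 (SSRI against other AD) has the same layout.

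**Objective 3.** The aim is descriptive: "To describe 1y mortality and readmission outcomes by plotting the cumulative incidence functions". The analysis restricts to patients not on an AD at admission and adds significance tests: "Log-rank tests will be used to examine mortality differences between AD treatment groups" and, for the other endpoints, "Gray tests will be used to test for differences between groups for these outcomes". It mentions neither weights nor hospital clustering.

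**Protocol, Statistical Considerations.** The general framework is propensity scoring, with logistic regression for dichotomous outcomes (mRS is an example), linear regression for continuous ones, and GEE for clustering within hospitals.

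**The concern.** The SAP's own reason for weighting in Objective 2 applies equally to Objective 6. Depression history is strongly related to AD prescription in the SAP's data, and it bears directly on PHQ-2, fatigue and quality of life. A raw comparison would mix any effect of the drug with the reason for prescribing it. With no analysis written down, the estimator, the covariates and the handling of mRS would also be chosen after the data are seen.

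Objective 3 raises a narrower version. Its p-values would be the only AD against no-AD evidence in AD-naive patients, and a reader may take them as a treatment comparison.

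**Working it through.** **1. The SAP's own figures reproduce** (II. Variables, Primary exposure variable). Depression history: 3,309/7,593 = 43.58% with AD; 1,032/21,584 = 4.78% without. Difference 0.388. AD share: 7,593/29,177 = 26.02%.

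**2. Objective 6: possible size of confounding.** Assumption: the prospective cohort (aged 18 or older) has the imbalance seen in the retrospective cohort (aged 65 or older). With no AD effect, spurious raw difference in a binary outcome = 0.388 × outcome gap by depression history. The documents do not give that gap; 10 to 30 points is assumed.

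- 10 points: 0.388 × 0.10 = 3.9 points
- 30 points: 0.388 × 0.30 = 11.6 points
- Gap needed to reach the 8% in the Prospective Power Analysis: 0.08/0.388 = 20.6 points

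For scale, assume the 2,000 enrolment target and 26.02% on AD: 520 and 1,480 patients. Half-width of the raw 95% interval = 1.96 × √[q(1−q)(1/520 + 1/1,480)], which is 4.0 points at prevalence q = 0.2 and 5.0 at q = 0.5, ignoring clustering. The 8% refers to the combined population of 5,000. On that base (1,301 and 3,699) the half-width is 2.5 to 3.2 points.

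**3. Objective 3: what is planned in AD-naive patients.** 1,836 + 20,601 = 22,437, of whom 8.18% are on AD. Objective 2 adjusts in the full cohort. In Objective 4, "we will repeat modeling of these associations by the following subgroups" covers age, sex, race, NIHSS and depression history. AD-naive is not among them, so no adjusted estimate in these patients is planned.

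**4. Objective 3: sensitivity of the log-rank test.** One-year mortality of 15 to 30% is taken from the Protocol's Introduction (stroke in general; assumed here). SE(log HR) = 1/√(deaths × 0.0818 × 0.9182), ignoring clustering.

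- 15%: 3,366 deaths, SE 0.0629, 80% power at exp(2.80 × 0.0629) = HR 1.19
- 30%: 6,731 deaths, SE 0.0445, 80% power at exp(2.80 × 0.0445) = HR 1.13

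**5. Illustration only.** Imbalance in the AD-naive group is not given. Assume one unadjusted factor with prevalence 5% without AD and p₁ with AD, hazard ratio h, and no AD effect. Spurious HR = (1 + p₁(h−1))/(1 + 0.05(h−1)).

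| p₁ | h | Spurious HR | Chance of p<0.05 at 15% / 30% mortality |
|---|---|---|---|
| 0.15 | 1.2 | 1.02 | 6% / 7% |
| 0.15 | 1.5 | 1.05 | 12% / 19% |
| 0.25 | 1.5 | 1.10 | 32% / 55% |
| 0.25 | 2 | 1.19 | 79% / 98% |
| 0.25 | 3 | 1.36 | over 99% / over 99% |

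A range from 6% to over 99% shows that moderate confounding could register. It does not say what will happen in this cohort.

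**6. Objective 7.** Depression history is 44.22% (SSRI) against 43.27% (other AD), a difference of 0.0095. The formula in step 2 gives 0.1 to 0.3 points. If the retrospective split holds (520 × 0.7062 = 368; 520 × 0.2938 = 153), the raw half-width is 7.5 to 9.4 points.

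**The case against.** **The Protocol already names the methods.** It does, and the SAP nowhere withdraws them, so a reader should not infer that the two documents contradict each other. But the Protocol's wording is general. It fixes no covariates, time points or mRS model for Objective 6, and the SAP is where these belong.

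**The tables do yield an association.** Partly right. Two means with standard errors give a crude difference and interval, so it would be wrong to say that no association can be obtained. What they cannot give is an adjusted one.

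**Objective 3 is descriptive.** Unadjusted curves with log-rank and Gray tests beside adjusted models are common practice. Objective 2 already gives weighted full-cohort results, with prior AD use among the listed covariates, and Objective 4 repeats the models by depression history. Restricting to AD-naive patients also removes the largest reported imbalance (prior AD use, 75.57% against 3.53%). All of this stands and makes the point secondary. That the tests are unadjusted is itself inferred from silence. It is the likelier reading, because the SAP says so where methods are to be repeated and here names different ones. What remains is a between-group p-value with no adjusted counterpart in the same patients.

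**The bias sizes rest on assumed inputs.** They do. The documents do not support a claim that the Objective 3 tests are biased by any stated amount.

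**Conclusion.** The main point holds: Objective 6 states an association as its aim, and the SAP plans only unadjusted group summaries for it. Under the stated assumptions (retrospective imbalance carried over, outcome gap of 10 to 30 points) the raw difference could be off by 3.9 to 11.6 points, which is of the same order as or larger than its sampling error. This should be fixed before analysis.

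The Objective 3 point also holds but is narrower, and its bias is unknown. Objective 7 is minor: the two reported variables are close to balanced (depression history as above; prior AD use 75.33% against 73.36%), so a reader should not infer confounding there. It lacks only a printed effect estimate.

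A reader might also infer that the antidepressant analysis as a whole, or the primary endpoint, is unadjusted. The documents do not support that: home-time and the clinical outcomes are covered by Objective 2.

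**What to change.** **Objective 6.** Add an Analysis paragraph that applies the Protocol's framework. For each patient-reported outcome at 3 and 6 months, give an IPW-weighted or covariate-adjusted effect with 95% interval, accounting for clustering by hospital. Fix the covariates in advance, including depression history, prior AD use, NIHSS and the Rankin at enrolment. State the mRS cut-off or ordinal model. Keep Tables 6A to 6G as description.

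**Objective 3.** Either re-estimate the weights in the AD-naive cohort and report weighted curves, an IPW Cox test with hospital-robust variance, and weighted one-year cumulative-incidence differences with intervals; or label the curves unadjusted and drop the p-values, for which one sentence is enough.

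**Objective 7.** Print an effect estimate with 95% interval, using a short covariate set fixed in advance because numbers are small.

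**Cost.** SAP wording and programming on variables already collected; no new data. Intervals will widen, weights may be extreme (only 8.2% of AD-naive patients are on AD), and unmeasured confounding remains.
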